## **6. ANALYSIS SETS**

### **6.1 Full Analysis Set**

This analysis set includes all enrolled subjects who are randomized.

Disposition data will be summarized and listed using the Full Analysis Set. The Full Analysis Set will be analyzed as randomized.

### **6.2 Safety Analysis Set**

This analysis set includes all enrolled subjects who receive at least one dose of active drug or placebo.

---

All safety, treatment exposure, demographic and baseline characteristic data, and efficacy data will be summarized and listed using the Safety Analysis Set. The Safety Analysis Set will be analyzed as treated.

### **6.3 Pharmacokinetic Analysis Set**

This analysis set includes all enrolled subjects who receive at least one dose of active drug (ARO-ENaC) and have measurable PK concentration data. Subjects may be excluded if they have protocol deviations which would impact PK analysis.

PK concentrations and parameters will be summarized and listed using the PK Analysis Set. The PK Analysis Set will be analyzed as treated.

## **7. PLANNED ANALYSES**

### **7.1 Data Safety Committee and Early Stopping Guidelines**

Escalation to the next cohort will proceed according to the study design until the highest planned dose cohort is completed, unless the trial is stopped early by the DSC, principal investigator (PI), or Sponsor. Dose escalation will require approval by the DSC based on evaluation of all available safety and, when available, PD data through at least Day 21 of the most advanced NHV cohort.

A decision to stop the trial early or discontinue drug in an individual subject, group of subjects or to halt enrollment temporarily or permanently may be indicated based on the stopping rules stated in the Protocol.

### **7.2 Interim Analysis**

For NHV Cohorts 1 to 5, interim analyses may occur after completion of each NHV cohort (after all subjects within a cohort complete or discontinue early). After completion of each cohort, the Sponsor will be unblinded and EMB may create unblinded TFLs.

For CF Cohorts 2b to 4b, interim analyses may occur when all subjects within each cohort complete their Day 37 visit (or discontinue early). EMB will create both blinded and unblinded TFLs. Unblinded TFLs will be kept in a secure location and will be handled and viewed only by designated unblinded personnel, independent of the study team. Designated unblinded personnel are documented in the Matrix of Access to Restricted Data. Blinded TFLs will be summarized by cohort, not separated by active and placebo arms. After completion of each CF cohort, the Sponsor may be unblinded to that cohort.

### **7.3 Primary Analysis**

Primary analysis will occur when all subjects in Cohort 6 have completed their Day 43 visit (or have discontinued early) and all other cohorts have completed. EMB and the Sponsor may be unblinded after the data have been entered and cleaned.

## 7.4 Final Analysis

Final analysis will occur upon completion of all cohorts in the study, after the study has been locked and all cohorts have been unblinded. The purpose of final analysis is to provide safety and efficacy analyses using complete study data.

## 8. DATA SCREENING AND ACCEPTANCE

### 8.1 Data Handling and Electronic Transfer of Data

The Sponsor will be responsible for providing all data to be used in the planned analyses. Data will be provided to EMB as Standard Data Tabulation Model (SDTM) datasets.

### 8.2 Handling of Missing and Incomplete Data

Missing values will not be imputed, except in the case of determining treatment-emergent status for AEs, concomitant status for medication and procedures, and for missing or partial dates where a complete date is required for calculations.

Missing	Imputation	Exception
Day	01	Default to Study Day 1 if an AE, medication/procedure starts the same year and month as Study Day 1 and the end date has same year and month as Study Day 1 or later.
Day / Month	01 / Jan	Default to Study Day 1 if an AE, medication/procedure starts the same year as Study Day 1 and the end date has same year as Study Day 1 or later.
Day / Month / Year	To calculate a missing start date: 

If a partial or complete stop date is present:

Stop date < first dosing date: impute January 1 of the stop year

Stop date <math>\geq</math> first dosing date: impute the date of first dose

If it is unknown whether the stop date is < or <math>\geq</math> first dosing date due to a missing or partial stop date, or if a stop date is not

	

	collected: impute date of first dose.	
--	---------------------------------------	--

Medications and procedures with missing or partial end dates will be assumed to be concomitant unless a partial end date documents it as ending prior to treatment.

The original missing or partial date, the imputed complete date, and an indicator variable that indicates which dates were imputed will be retained in the database. Dates will be presented as collected in all listings. Imputed dates will not be presented in listings but may be used for summary tables.

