11. ADVERSE EVENTS

The PI and clinical facility staff are responsible for detection, recording and reporting of events that meet the criteria and definition of various AEs as listed below. Adverse events will be recorded from time of signed consent through to EOS; only AEs that occur post-dose will be considered treatment-emergent. The PI and clinical facility staff are responsible for detection, recording and reporting of pregnancy and appropriate follow up. Any known pregnancy that occurs within 90 days following the end of study visit should be reported by the subject to the PI. Information regarding any reported pregnancy should be collected for at least 1 year after birth or longer if it is decided that additional follow-up is required or until the end of the pregnancy.

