## 5. DEFINITIONS

### Study Day:

Day of study relative to the date of first dose of active drug or placebo. First dose date will be considered as Day 1. Calculated prior to first dose date as (date of measurement – date of first dose) and calculated after first dose date as (date of measurement – date of first dose + 1).

Baseline:

The last observation prior to the first dose of active drug or placebo. The baseline value may be an unscheduled or repeated measurement.

Change (absolute) from baseline:

The arithmetic difference between a post-baseline value and baseline for a given time point: change (absolute) from baseline = (post-dose value – baseline value).

Percent change from baseline:

The percent change between a post-baseline value and baseline for a given time point: [(post-dose value – baseline value) / baseline value] \*100%

Treatment-emergent AEs (TEAEs):

TEAE will be derived as any AEs occurring on or after the first dose.

Treatment-emergent SAEs (TESAEs):

TESAE will be derived as any serious AEs occurring on or after the first dose.

Concomitant Medications:

Concomitant medications will be derived as any medications with an end date on or after the first dose.

Use of medications at baseline:

For each of the following medications: CFTR modulators, inhaled hypertonic saline, inhaled bronchodilators, chronic inhaled antibiotics, inhaled corticosteroids, dornase alfa, and azithromycin, any use within 30 days prior to first dose will be considered as use at baseline. Dornase alfa and azithromycin will be identified by the Preferred Drug Name as coded by WHODrug. All other medications will be identified as recorded on the CF-Concomitant Medications eCRF.

Sputum pseudomonas status at baseline:

Any pseudomonas (as collected on the Airway Infection eCRF) present within 30 days prior to first dose will be considered as positive at baseline.

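### SAP 8.2 tests an adverse event's end date against the month or year of Study Day 1, not the dosing date: some events that ended before dosing become TEAEs, and ongoing events with a partial start have no explicit rule

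*SAP*

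**What the plan says.** Protocol 12.8 leaves the imputation of partial adverse event dates to the SAP. SAP 8.2 rules out imputation in general, "except in the case of determining treatment-emergent status for AEs" and a few similar uses, and gives a three-row table.

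- **Only the day missing.** Impute 01. Use Study Day 1 instead if the event "starts the same year and month as Study Day 1 and the end date has same year and month as Study Day 1 or later".
- **Both day and month missing.** Impute 01 January. Use Study Day 1 instead if the event "starts the same year as Study Day 1 and the end date has same year as Study Day 1 or later".
- **Start wholly missing.** Compare the stop date with the first dosing date. If it is earlier, "impute January 1 of the stop year"; if it is the same or later, use the date of first dose. If the order cannot be determined "due to a missing or partial stop date, or if a stop date is not" recorded, use the date of first dose.

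Below the table there is a convention for unknown end dates, but not for adverse events: "Medications and procedures with missing or partial end dates will be assumed to be concomitant", with an exception where a partial end date shows otherwise.

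SAP 5 then classifies on onset alone: "TEAE will be derived as any AEs occurring on or after the first dose". Pre-dose events are in the database, because Protocol 11 states: "Adverse events will be recorded from time of signed consent through to EOS". Protocol 10.2 allows screening up to 28 days before dosing.

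**The concern.** The first two rows ask whether the event ended in or after the calendar month (or year) of Study Day 1. The question that matters is whether it ended before the first dose. Where a known end date falls in that month or year but before dosing, the SAP ignores evidence that proves the event was pre-dose.

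The same two rows say nothing about an event with no end date. Taken literally the exception fails, and the event is dated to the first of the month or year, normally before dosing. Unresolved events are ones a safety reader particularly wants to see.

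The third row handles both situations sensibly. Knowing the month or year of onset can therefore give a worse classification than knowing nothing about onset. At stake are the TEAE and TESAE tables by system organ class, preferred term, severity and relationship, which carry most of the reporting on a safety primary endpoint in small cohorts.

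**Working it through.** There is no plan figure to reproduce; the check applies the rule as written.

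**Inputs.** Imputation table: SAP 8.2. TEAE if the (imputed) start is on or after first dose: SAP 5. Collection from consent: Protocol 11. Screening window of 28 days: Protocol 10.2. Planned active subjects per cohort: Protocol Table 4. The Study Day 1 date of 20 May is illustrative.

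**Worked cases, Study Day 1 = 20 May**

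| Recorded start | Recorded end | Imputed start | Class | Comment |
|---|---|---|---|---|
| ?? May | 10 May | 20 May | TEAE | Wrong: start is 20 − 10 = 10 days after the end |
| Year only | 28 April | 20 May | TEAE | Wrong: start is 2 + 20 = 22 days after the end |
| ?? May | none (ongoing) | 1 May | pre-dose | Wrong if true onset was 20 May or later |
| Year only | none (ongoing) | 1 January | pre-dose | Wrong if true onset was 20 May or later |
| Wholly missing | 10 May | 1 January | pre-dose | Right (row 3) |
| Wholly missing | none (ongoing) | 20 May | TEAE | Conservative (row 3) |

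**Controls.** ?? June, ongoing, gives 1 June: TEAE, right. ?? April ending 10 May gives 1 April: pre-dose, right. ?? May ending 25 May gives 20 May: TEAE, the usual conservative result. If Study Day 1 is the first of a month, a missing day causes no error in either direction.

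**How often the rule errs, given a partial start.** The rule was applied to every possible Study Day 1 in one calendar year (2021). Onset dates ran from 28 days before dosing to end of study (Day 29 for healthy volunteers, Day 113 for CF patients), and all onset and end dates were weighted equally. Those weights are assumptions, not trial data.

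| Situation | Day missing | Day and month missing |
|---|---|---|
| Ended before dosing, called TEAE | 37.5% | 94.8% |
| Ongoing, true onset after dosing, called pre-dose, healthy volunteers (literal reading) | 50.7% | 95.9% |
| Same, CF patients | 13.0% | 84.4% |
| Ongoing errors if ongoing is read as a later end date | 0% | 0% |

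**Size for one subject.** The change in incidence is 1/n, and only if that subject has no other TEAE:

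- n = 4 (Cohorts 1–4, 2b, 3b): 1/4 = 25 points
- n = 8 (Cohort 5): 1/8 = 12.5 points
- n = 9 (Cohort 4b): 1/9 = 11.1 points
- n = 18 (Cohort 6): 1/18 = 5.6 points

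SAP 9 groups subjects by dose and regimen. If Cohorts 4 and 5 receive the same dose they share a column, n = 4 + 8 = 12, and the step is 1/12 = 8.3 points.

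**The case against.** The case for leaving the rule alone has real content, and several stronger readings that a reader might infer are not supported.

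- **That misclassification is certain in both directions.** It is certain only where a known end date precedes dosing. An ongoing event starting in an unknown day of May may truly have begun on 1–19 May, in which case 1 May classifies it correctly. A programmer might also read ongoing as later, and the second error then disappears. This stands: the second direction is a missing branch, wrong on a literal reading, and not a proven loss of events. It still needs writing down, because the only convention for missing end dates outside row 3 covers medications and procedures.
- **That the year-level exception captures events that ended months before dosing.** Adverse events start at consent and screening is within 28 days of dosing; earlier conditions are medical history (Protocol 11.3). Weeks is the realistic scale.
- **That the listings will show negative durations.** Using the imputed start in the first case gives 10 − 20 + 1 = −9 days. But SAP 8.2 lists dates as collected, and neither document says that duration uses imputed starts.
- **That the primary endpoint as a whole is misclassified.** It is worded as adverse events. The SAP 9.5.1 overall summary counts all AEs and SAEs, and all AEs are listed; none of that changes.
- **That the 1/n figures show expected impact.** They are the step for one subject. If the subject has another TEAE, only a term-level row or an event count changes.

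Finally, calling a pre-dose event treatment-emergent errs in the cautious direction. That is fair when timing is unknown, but not when the recorded end date settles it.

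**Conclusion.** The concern holds in a limited form. For a known end date before first dose but within the Study Day 1 month (or year), SAP 8.2 produces a start later than the recorded end and a false TEAE; this needs no interpretation. For ongoing events with a partial start in that month or year, the literal text gives a pre-dose date, the reverse of row 3, and can remove true TEAEs. That part depends on the reading and on the unknown true onset.

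The exposure is confined to TEAE and TESAE outputs and to partial starts in the Study Day 1 month or year. The documents give no frequency of partial dates, so the total effect is unknown and may be small. A single affected subject with no other TEAE shifts a cohort's incidence by 5.6 to 25 points at the planned active sizes. This should be corrected because the rule is definite, wrong, and cheap to repair.

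**What to change.** In both exceptions, keep the requirement that the partial start shares the Study Day 1 month (or year) and replace the end-date test. Impute Study Day 1 unless the complete or partial stop date shows that the event ended before the first dosing date; in that case keep the 01 (or 01 January) default. State that, for adverse events, ongoing, missing or ambiguous stop dates are treated as not ended before first dose.

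Under the enumeration above, both error rates fall to 0%. The price is that some ongoing events that truly began in screening will count as TEAEs: 52.3% of them with the day missing and 96.0% with day and month missing, under the same equal-weight assumption. That is the usual conservative convention and matches row 3.

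The cost is two table cells, one sentence and the matching derivation code, with no new data, best done before database lock. Any outputs already produced under the present rule would need the TEAE flag rederived.

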### **8.3 Outliers**

Descriptive statistics may be used to identify outliers of key variables. However, no statistical analysis or adjustment for outliers is planned; outliers will not be omitted from summaries.

### **8.4 Distributional Characteristics**

Before implementation of parametric methods of analysis, the distribution of analysis variables will be examined to determine if model assumptions are satisfied. Transformations or nonparametric methods of analysis may be used if warranted. However, in some cases, nonparametric analysis may be the initially proposed method due to the expected distribution of response. Whenever alternative methods of analysis are required, the description of the new method along with the rationale for its use will be documented in the CSR.

### **8.5 Validation of Statistical Analyses**

All computations for statistical analyses will be performed using SAS® software Version 9.4 or later. All SAS programs used in the production of statistical summary outputs will be validated with independent programming prior to finalization. In addition, all program outputs will be independently reviewed. The validation process will be used to confirm that all data manipulations and calculations were accurately done. Once validation is complete, a statistical reviewer will perform a final review of the documents to ensure the accuracy and consistency with this plan and consistency within tables. Upon completion of validation and quality review procedures, all documentation will be collected and filed by the project statistician or designee.

## **9. STATISTICAL METHODS OF ANALYSIS**

For all summary tables and figures described in this SAP, NHV Cohorts 1-5 and CF patient Cohorts 2b-4b and 6 will be summarized separately. Subjects will be grouped by dose and dosing regimen within each table and figure, with subjects receiving placebo pooled across cohorts. All data will be combined in listings, which will be sorted by cohort and subject number.

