Blood samples will be collected from each subject for metabolic analysis per the SOA. Samples will be frozen at -80°C for analysis outside of this study.

Urine collections will be performed after dosing per the SOA.

Data Analysis:

Healthy volunteers and CF patients will be analyzed separately.

For each healthy volunteers and CF population, subjects will be analyzed by cohorts. Placebo subjects from each cohort will be pooled. In addition, CF patients will also be analyzed in aggregate and separately based on CFTR mutation status and based on use or no use at baseline of a stable regimen (last 2 months) of CFTR modulators/correctors as well as use or no use at baseline of inhaled hypertonic saline.

Screening, Compliance, Tolerability and Safety Data:

In general, safety analyses will be performed based on Safety Analysis Set, which includes all enrolled subjects who receive at least one dose of study drug (placebo or active). Post-dose safety assessments will be compared with measurements recorded at baseline. Treatment-emergent AEs will be summarized using the Medical Dictionary for Regulatory Activities (MedDRA) under version 23.0 or later by System Organ Class (SOC) and Preferred Term (PT). The incidence and frequency of treatment-emergent AEs, SAEs, related AEs, related SAEs, and AEs leading to discontinuation, will be summarized by cohort per SOC, PT, and severity. All AEs, SAEs will also be presented in listings. The duration of AEs will be determined and included in listings, along with the action taken and outcome. The incidence of laboratory abnormalities will be assessed using descriptive summary statistics and shift tables. Vital sign measurements will be summarized at each scheduled time point using descriptive statistics. Abnormal physical examination findings will be summarized by time point and presented in subject listings. ECG parameters, changes from baseline, and qualitative assessments will be summarized. Pregnancy and FSH test results will be listed separately.

Pharmacokinetics:

Plasma concentrations of ARO-ENaC product constituents will be used to calculate the following PK parameters:

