ECG ⁴	X	X		X	X	X	X	X	X	X	X	X
Vital Signs (BP, temp, pulse ox., RR, heart rate) perform before other evaluations	X	X		X	X	X	X	X	X	X	X	X
Clinical Labs (heme, coag, chem, UA, Urine electrolytes)	X	X		X (pre-dose)	X (pre-dose)	X (pre-dose)	X		X	X	X	X
PK ²				X	X	X	X	X				
Plasma metabolite ID				X	X	X	X		X	X		
Urine collection for excretion and metabolite ID ³						X	X					
Chest X-ray (PA and Lateral) ⁵	X									X	X	X
Spirometry ¹	X	X							X	X	X	X
Concomitant Meds/Therapies	X	X							X	X	X	X
Adverse Events	X	X							X	X	X	X
Dose Administration (PBO or Active)												
Urine Cotinine	X											
Anti-drug antibodies		X									X	

1. On dosing days (Days 1,2,3), completed at immediate pre-dose, 15 min (± 10 min), 60 min (± 10 min), 120 min (± 10 min). On non-dosing days, only completed once per visit.
2. Plasma PK collected:
 - a. Day 1: Pre-dose, then based on start of inhalation 30, 60, 120 min, 4, 6, 8, 16 hours.
 - b. Day 2: Pre-dose (Day 1, 24 hr timepoint), then based on start of inhalation, 1, 2, 4 hours
 - c. Day 3: Pre-dose (Day 2, 24 hr timepoint), then based on start of inhalation, 30, 60, 120 min, 4, 6, 8, 16, 24 (on Day 4), 48 hours (on Day 5).
3. Urine collected cumulatively from 0-6 hours and 6-24 hours post dose on Day 3 through Day 4. Subject should void pre-dose on Day 3. Metabolite ID will be performed on urine samples collected (pooled analysis).
4. On dosing days, ECG performed pre-dose (-4hrs) and 2 hours (± 10 min) post-dose; any abnormal ECG's will be repeated in triplicate with each measurement approximately 1 minute apart.
5. Chest x-ray to be performed at screening, day 15, and day 29 (or early termination). At all other times, any AE consistent with lower respiratory infection, dyspnea, or bronchospasm will trigger a chest X-ray and PFT measurement.

Note: R = randomize.

Table 1.2: Cohort 5:

Assessment	Screen	Day 0 Confine	R	Day 1	Day 2	Day 3	Day 4	Day 5	Day 8	Day 18	Day 19	Day 29 EOS	Early Term.
Visit Windows	Days -28 to -1			± 5 min for 30 min post dose PK draw and ± 10 min for all other post dose PK timepoints only					± 2 d	± 3 d	+ 2d	± 2 d	
Informed Consent	X												
Eligibility Criteria	X												
Body Mass Index/Weight/Height	X			X					X	X		X	X
Demographics	X												
Medical History	X												
Drug Screen	X												
Hepatitis/HIV Serology Screen	X												
Physical Exam (may be symptom directed after Day 1)	X	X		X (pre-dose)	X	X	X	X	X	X		X	X
FSH (in women of post-menopausal age only)	X												

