Urine qualitative pregnancy test	X			X (pre-dose)								X	X
ECG ³	X			X	X	X	X	X	X	X		X	X
Vital Signs (BP, temp, pulse ox., RR, heart rate) perform before other evaluations	X	X		X	X	X	X	X	X	X		X	X
Clinical Labs (heme, coag, chem, UA, Urine electrolytes)	X			X (pre-dose)	X (pre-dose)	X (pre-dose)	X		X	X		X	X
PK ²				X	X	X	X	X					
24 hour urine labs ⁶				X						X		X	
Chest X-ray (PA and Lateral) ⁴	X									X		X	X
Spirometry ¹	X			X	X	X	X		X	X		X	X
Concomitant Meds/Therapies	X	X		X	X	X	X	X	X	X	X	X	X
Adverse Events	X	X		X	X	X	X	X	X	X	X	X	X
Dose Administration (PBO or Active)				X	X	X							
Urine Cotinine	X												
Anti-drug antibodies				X								X	
Bronchoscopy with bronchoalveolar lavage and bronchial brushing ⁵				X						X			
Phone Call											X		

1. On dosing days (Days 1,2,3), completed at immediate pre-dose, 15 min (± 10 min), 60 min (± 10 min), 120 min (± 10 min). On non-dosing days, only completed once per visit.
2. Plasma PK collected:
 - a. Day 1: Pre-dose, then based on start of inhalation 30, 60, 120 min, 4, 6, 8, 16 hours.
 - b. Day 2: Pre-dose (Day 1, 24 hr timepoint), then based on start of inhalation, 1, 2, 4 hours
 - c. Day 3: Pre-dose (Day 2, 24 hr timepoint), then based on start of inhalation, 30, 60, 120 min, 4, 6, 8, 16, 24 (on Day 4), 48 hours (on Day 5).
 - d. Plasma metabolite identification may be performed on PK samples at the Sponsor's discretion
3. On dosing days, ECG performed pre-dose (-4hrs) and 2 hours (± 10 min) post-dose; any abnormal ECG's will be repeated in triplicate with each measurement approximately 1 minute apart.
4. Chest x-ray to be performed at screening, day 18, and day 29 (or early termination). At all other times, any AE consistent with lower respiratory infection, dyspnea, or bronchospasm will trigger a chest X-ray and PFT measurement. Day 18 chest X-ray is to be completed within the associated visit window and prior to bronchoscopy.
5. All eligibility requirements (inclusion and exclusion criteria) must be met prior to a subject undergoing bronchoscopy. On days when bronchoscopy is performed, all other assessments will be performed prior to bronchoscopy. Vital signs will be repeated during recovery from sedation post-bronchoscopy at the frequency deemed appropriate by the site.
6. 24 hour urine collection to be completed prior to dose administration on day 1. For visits not associated with confinement, 24 hour urine is to be collected by the subject at home.

Note: R = randomize.

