It is important to note that while weight-based safety margins are calculated based on animal PDD compared to human RDD or DD, the RDD and DD are **not** the dose loaded into the nebulizer device. The nebulizer loaded dose required to achieve a certain RDD depends on the efficiency of the nebulizer. A table converting RDD into actual nebulizer loading dose is provided (**Table 3**).

Table 3: Nebulizer loaded dose for each cohort

Cohort	Nebulizer Loaded Dose	Concentration	Loaded Volume for Nebulization	Approximate Nebulization Time	Calculated Respirable Delivered Dose (RDD)
1	20 mg	10 mg/mL	2.0 mL	3-5 min	2.9 mg
2	40 mg	10 mg/mL	4.0 mL	6-8 min	6.6 mg
2b	40 mg	10 mg/mL	4.0 mL	6-8 min	6.6 mg
3	65 mg	10 mg/mL	6.5 mL	13-15 min	12.5 mg
3b	65 mg	10 mg/mL	6.5 mL	13-15 min	12.5 mg
4	180 mg	40 mg/mL	4.5 mL	10-12 min	30.7 mg
4b	180 mg	40 mg/mL	4.5 mL	10-12 min	30.7 mg
5*	180 mg	40 mg/mL	4.5 mL	10-12 min	30.7 mg
6*#	490 mg (245 mg)	40 mg/mL	12.2 mL (6.1 mL)	30 min (15 min)	92.1 mg (46 mg)

*Doses for cohorts 5 and 6 represent the maximum potential dose, which may be decreased at the decision of the sponsor, based on existing data from prior cohorts.

*#Cohort 6 dose will require 2 nebulizations. Top line indicates total quantity and bottom line indicates quantity per nebulization (in parentheses)

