Following an affirmative vote from the DSC meeting held during NHV cohort 4 allowing the opening of CF Cohort 4b, NHV cohort 5 may be subsequently opened for accrual. The primary purpose of cohort 5 will be to assess the effect of ARO-ENaC on α ENaC mRNA expression, with samples obtained via bronchoscopy. The dose in cohort 5 will be equivalent to or less than the dose utilized in cohort 4. Based on available safety data reviewed during prior DSC meetings, the Sponsor or DSC may adjust the dose in cohort 5 downward.

The DSC will consist of at least one study Investigator, Sponsor Medical Monitor, Sponsor pharmacovigilance lead, and an independent physician experienced in pulmonary drug development and/or early stage clinical trials.

Cystic Fibrosis Patients:

Cohorts 2b, 3b, 4b will enroll eligible CF patients who have signed an IRB/EC approved informed consent form to receive two cycles of ARO-ENaC or PBO administered daily on Days 1, 2 and 3, then again on Days 22, 23 and 24. Screening for the CF cohorts can begin once Cohort 2 dosing has commenced but dose administration may not proceed until after the DSC has opened the designated CF patient cohort. CF patient cohorts 2b, 3b, and 4b will be opened for accrual once the corresponding NHV cohort receiving the same dose level has reached Day 21 and based on DSC vote that it is safe to proceed. CF patient cohorts 2b, 3b, and 4b will enroll in sequence with 2b enrolling first, followed by 3b and then Cohort 4b.

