12.3. Safety/Tolerability Data

In general, safety analyses will be performed based on Safety Analysis Set, which include all enrolled subjects who receive at least one dose of study drug (placebo or active). Results will be summarized by population (NHV and CF) and cohort. Placebo subjects from each cohort will be pooled by population.

Treatment-emergent AEs will be summarized by System Organ Class (SOC) and Preferred Term (PT), classified from verbatim terms, with MedDRA version 23.0 or later. The incidence and percentage of participants with at least 1 occurrence of a PT will be included, per the most severe grade using a 3-point scale (mild, moderate, severe). The number of events per Preferred Term will also be summarized. Causality (relationship to study treatment) will be summarized separately.

The incidence and frequency of treatment-emergent AEs, SAEs, related AEs, related SAEs and AEs leading to withdrawal, dose modification, or treatment discontinuation will be summarized by population and cohort by SOC and Preferred Terms. All AEs, SAEs will also be summarized in listings. The duration of AEs will be determined and included in listings, along with the action taken and outcome.

Laboratory parameters will be summarized at each scheduled time point using descriptive statistics. The incidence of laboratory abnormalities will be summarized. Results for variables that are not coded will be presented in the listings as “below, within, and above” the normal limits of the laboratory. Pregnancy test results will be listed.

Vital sign measurements will be summarized at each scheduled time point using descriptive statistics. Physical examination findings will be summarized by time point and presented in patient listings.

ECG parameters at each scheduled study visit, changes from baseline and qualitative assessments will be summarized.

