### 10. CHANGES FROM PROTOCOL-SPECIFIED ANALYSES

There are no major changes between the protocol-defined statistical analyses and those presented in this statistical plan.

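### SAP Section 9 groups healthy-volunteer safety data by dose where the protocol groups by cohort, without declaring it; at equal dose, Cohorts 4 and 5 share a column although their visits and procedures differ

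*SAP*

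**What the plan says.** The protocol synopsis, under Data Analysis, states: "For each healthy volunteers and CF population, subjects will be analyzed by cohorts. Placebo subjects from each cohort will be pooled". Protocol Section 12.3 repeats this for safety: "Results will be summarized by population (NHV and CF) and cohort. Placebo subjects from each cohort will be pooled by population".

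SAP Section 9 sets a different rule for all summary tables and figures: "Subjects will be grouped by dose and dosing regimen within each table and figure, with subjects receiving placebo pooled across cohorts". SAP Section 10 then states: "There are no major changes between the protocol-defined statistical analyses and those presented in this statistical plan".

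The protocol does use dose for some outputs. Section 12.5 tabulates PK parameters by dose level, Section 12.4 summarises anti-drug antibody changes by dose, and the synopsis allows antibody shift tables by cohort or by dose. The mismatch therefore concerns the other safety summaries: adverse events, laboratory tests, vital signs, ECG and healthy-volunteer spirometry.

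On dose, Protocol Section 7.1 says: "The dose in cohort 5 will be equivalent to or less than the dose utilized in cohort 4". Table 3 in Section 5.8 lists both cohorts at 180 mg loaded (30.7 mg respirable delivered dose), with the footnote: "Doses for cohorts 5 and 6 represent the maximum potential dose, which may be decreased at the decision of the sponsor".

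The visit schedules differ. The chest X-ray notes show it. Table 1.1 (Cohorts 1-4) has "Chest x-ray to be performed at screening, day 15, and day 29 (or early termination"; Table 1.2 (Cohort 5) has "Chest x-ray to be performed at screening, day 18, and day 29 (or early termination". Only Cohort 5 undergoes bronchoscopy, at baseline and at Day 18 (synopsis; SAP Section 9.6.6).

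**The concern.** If Cohort 5 is given Cohort 4's dose, the SAP rule puts both active arms in one column, although the protocol makes them differ in two ways.

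- **Visits.** Cohort 4 is seen at Day 15 and not Day 18; Cohort 5 is seen at Day 18 and not Day 15. Laboratory and spirometry results are tabulated by scheduled visit or timepoint, and mean potassium, sodium, FEV1 and ppFEV1 are plotted by study day (SAP Sections 9.5.2 and 9.6.1). In a merged column, the Day 15 and Day 18 rows come from different people.
- **Procedure.** SAP Section 5 counts any event on or after first dose as treatment-emergent. That includes events after the Day 18 bronchoscopy, and events from the baseline bronchoscopy that begin once dosing has started. These would be counted with the 180 mg group.

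Adverse-event incidence is the primary endpoint, and serum electrolytes and FEV1 in healthy volunteers are secondary safety endpoints. A change of subjects, or a procedure effect, could be misread as an effect of the top healthy-volunteer dose.

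**Working it through.** **1. The plan's own figure.** Protocol Table 5 sizes the cohorts by the chance of at least one TEAE, 1 - (1 - p)^n. For p = 0.2 / 0.3:
- n = 4 (Cohort 4 active): 0.5904 / 0.7599, stated as 0.59 / 0.76.
- n = 8 (Cohort 5 active): 0.8322 / 0.9424, stated as 0.83 / 0.94.

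Both reproduce, so the cohort is the unit of the size rationale. A merged n = 12 gives 0.93 / 0.99.

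**2. Where the two rules differ.** SAP Section 9 keeps healthy volunteers and CF patients apart. At the Table 3 doses each CF cohort has its own dose and regimen, and healthy-volunteer Cohorts 1, 2 and 3 have 20, 40 and 65 mg. Only Cohorts 4 and 5 coincide (180 mg, Days 1-3). A lowered Cohort 5 dose would separate them.

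**3. Planned counts by visit (Tables 1.1 and 1.2), equal dose.**

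| Column | Day 8 | Day 15 | Day 18 | Day 29 |
|---|---|---|---|---|
| Merged 180 mg active (4 + 8) | 12 | 4 | 8 | 12 |
| Pooled placebo (4 x 2 + 4) | 12 | 8 | 4 | 12 |
| Each lower dose, active | 4 | 4 | 0 | 4 |

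The switch in the active column comes from the SAP grouping. The switch in placebo comes from pooling that both documents plan.

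**4. Noise in the Day 15 to Day 18 difference.** It compares 4 subjects with 8 others.
- Raw values: SE = sqrt(1/4 + 1/8) = 0.612 SD.
- Change from baseline: SE = 0.612 x sqrt(2(1 - r)) SD, with r the assumed baseline-to-visit correlation. r = 0.8 gives 0.39; r = 0.9 gives 0.27; r = 0.5 gives 0.61.
- The documents give no between-subject SD for healthy volunteers. At an assumed ppFEV1 SD of 10 to 15 points, this is 6.1 to 9.2 points for raw values, and 3.9 to 5.8 points for change at r = 0.8.

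**5. Bronchoscopy share.** Merged 180 mg active 8/12; pooled placebo 4/12; each lower dose 0/4. All active against all placebo is balanced: 8/24 and 4/12.

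**6. Expected adverse-event shift with no drug effect.** Let b be background risk and q the added procedure risk. A bronchoscoped subject's risk rises by (1 - b)q. Merged minus placebo is (1 - b)q x (8/12 - 4/12) = (1 - b)q/3; merged minus a lower dose is 2(1 - b)q/3. Protocol Section 5.7 gives 0.6% for the most common complication and 0.1 to 0.2% each for two severe ones. As a higher assumption, give all six listed complications 0.6% and both severe ones 0.2%: 6 x 0.6% + 2 x 0.2% = 4.0%.

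| b = 0.30 | q | v placebo (points) | v lower dose (points) |
|---|---|---|---|
| One procedure, 0.6% | 0.006 | 0.14 | 0.28 |
| One procedure, 4.0% | 0.04 | 0.93 | 1.87 |
| Two procedures, 0.6% each | 0.01196 | 0.28 | 0.56 |
| Two procedures, 4.0% each | 0.0784 | 1.83 | 3.66 |

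At b = 0.20, two procedures give 0.32 to 2.09 points against placebo. Counting the baseline procedure in full overstates it, because its pre-dose events are not treatment-emergent. One subject in 12 is 8.3 points.

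**The case against.** The case for leaving the plan alone is substantial. The protocol itself uses dose for PK and antibody data, SAP Section 10 denies only major changes, and the merge is conditional on equal dose. Several safeguards exist:

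- Every continuous summary shows n (SAP Section 9.1), so 12, 4, 8, 12 would be visible.
- Treatment-related TEAEs are tabulated separately (SAP Section 9.5.1), and Protocol Section 11.5.2 classes an event with a clearly likelier alternative cause as not related.
- Listings are sorted by cohort, and interim outputs may follow each healthy-volunteer cohort (SAP Section 7.2).
- Day 18 assessments precede that day's bronchoscopy (Table 1.2, note 5).
- No hypothesis is tested (SAP Section 2.2), healthy-volunteer escalation precedes Cohort 5, and CF tables are unaffected.

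All of this stands, and it limits the point to a cheap improvement. It does not remove the mismatch: the safety summaries are by cohort in one document and by dose in the other, and nothing says so.

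A reader might infer more than the documents support:

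- **That merging loses precision against following the same 12 subjects across Days 15 and 18.** No grouping offers that comparison, because neither cohort has both visits. With cohort columns the step simply disappears.
- **That the FEV1 endpoint is blurred by 6 to 9 points.** That range is for raw ppFEV1. The endpoint is change from baseline, where the figure is smaller at r = 0.8 or above.
- **That the plots will draw a false trend line.** The SAP does not say whether means are joined, and the table and figure shells are in a companion document not available here. They may already separate the cohorts.

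**Conclusion.** The mismatch is real but narrow. Safety summaries are by cohort in the protocol and by dose and regimen in the SAP, undeclared, and the difference matters only for healthy-volunteer Cohorts 4 and 5 at equal dose. In that case a Day 15 to Day 18 difference in the merged column is between different subjects. It is noise that could be read as a time trend, not a bias.

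The adverse-event mix does have a direction, against 180 mg. Its expected size at the stated complication rates is about 0.1 to 2 points against placebo, less than one subject in 12, so a claim of material distortion is not supported. This rests on an assumed background risk of 20 to 30% and on rates that can err either way: they do not cover all procedure events, while Section 5.7 expects lower risk in healthy volunteers than in patients with respiratory disease. No decision rests on the merged column.

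**What to change.** In SAP Section 9, for healthy-volunteer safety tables and plots:

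- Show Cohort 4 active (n = 4) and Cohort 5 active (n = 8) as separate columns, as the protocol specifies.
- Place a Cohort 5 placebo column (n = 4) beside Cohort 5 active. Cohort 4 against Cohort 5 active then shows the procedure at equal dose, and Cohort 5 active against its own placebo shows the drug with the procedure in both arms.
- Keep the combined 180 mg and fully pooled placebo columns for adverse-event incidence as additional columns. Do not use the combined column for the Day 15 and Day 18 rows or plot points.
- If any by-dose grouping of safety data is kept, state it in SAP Section 10.

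The cost is a few extra small columns and no new data. No precision is lost for incidence: at 30% risk the retained 12 v 12 comparison has SE sqrt(0.21/12 + 0.21/12) = 18.7 points. The added 4 v 8 and 8 v 4 contrasts have SE sqrt(0.21/8 + 0.21/4) = 28.1 points, so they can be read descriptively only.
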